C2) Population to be studied: Women between 9 to 19 weeks pregnant with a BMI 18.5 – 45.0 kg/m² and between the ages of 18-45 years will be recruited from the University of Kansas Medical Center (KUMC) OB clinics. We will enroll all race/ethnic groups. Participant's routine OB care will be managed by their primary Obstetrician. Any interventions, laboratory or other evaluations, and decisions regarding delivery will be made by the primary Obstetrician. Groups of 6-10 subjects will be block randomized to control or the intervention group to ensure adequate size for optimal group dynamics. The intervention will start at 12-20 wks and last 18 weeks, ensuring intervention completion by 38 weeks in pregnancy. We will screen women to determine the current dietary fiber intake. If they are consuming 25 g/day of fiber or more, they will be excluded from the study. Women who do not have internet and phone access will be excluded from the study. Participants must be willing to consume provided snacks. Participants will also be excluded if they have history of gestational diabetes (GDM), diabetes, pre-eclampsia, hypertension, heart disease, hypothyroidism, or other metabolic abnormalities, current hyperemesis gravidarum, eating disorder, smoking, or are pregnant with multiples. Women that develop any of these medical conditions during pregnancy will be accounted for in the final analysis. Deviations from inclusion criteria will be at the discretion of the PI.

C3) Recruitment: We have access to the electronic clinic schedule, therefore we have the exact date and time of the recruit's OB visit. We have worked directly with physicians and staff providing an in service at meetings to ensure a smooth recruiting process so that we do not impede clinic flow. Annually, 1800 women are managed in the OB clinics at KUMC. Additionally, we will recruit using an electronic flyer via social media. Individuals who have agreed to future contact from previous studies will also be approached if eligible via email or phone.

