C5e) **Usual care group:** Those randomized to the UC group will be cared for by their obstetrician using standard treatment. Standard treatment consists of attending regularly scheduled visits where patients are weighed and evaluated. The standard visit schedule is once monthly until 32 wks gestation, bi-weekly for 32-37 wks gestation, weekly until delivery, and at 6 wks post-partum. At the first prenatal visit, they will receive the standard nutrition and physical activity counseling along with literature outlining recommendations provided by the obstetrics team. Women in the UC group will report body weight weekly via REDCap. In the multiple goal pilot study, the control group reported body weight weekly. This minimal contact did not impact the rate of excessive GWG, as the rate of excessive GWG in the control group was 78%.

C5f) **Adherence:** Adherence will be assessed based on participants meeting their prescribed fiber goal (≥ 30 g/day average) as well as by call attendance $\geq 75\%$ (14 or more calls attended). Starting in week two of the intervention, one 24-hour dietary recall will be collected every two weeks (9 recalls total) to determine fiber intake. Participants will be considered adherent if their number of days meeting fiber goal/number of days reported is $\geq 75\%$.

C6) **Standard training and quality assurance:** [name] has considerable experience (over 10 years) delivering weight management interventions and as a trainer (R01 DK076063, HL11842, DK094833). [name] will provide initial and ongoing training for the Dietitians who will lead the group sessions. [name] will randomly select 20% of the calls and using the checklist, make sure $>80\%$ of the content was covered. If $>80\%$ of the content was not covered, the Dietitian will be re-trained focusing on deficient areas.

C7) **Maternal & infant assessments:** Listed in **Table 4** is an outline of study visits and procedures. In C7a-i, details are provided regarding maternal & infant outcomes that will be collected.

Table 4. An outline of study visits and procedures.

Study procedure	During Pregnancy		Postpartum			
	Baseline: 12-20wks	End of Intervention: 30-38wks	2 weeks	2 months	6 months	12 months
Questionnaires	•	•	•	•	•	•
Maternal anthropometrics	•	•	•	•	•	•
Maternal body composition (BodPod, BIA)	•	•		•	•	•
Maternal vitals	•	•	•	•	•	•
Maternal pregnancy test			•	•	•	•
Maternal DXA scan				•	•	•
Maternal diet recalls	•	•	•	•	•	•
Maternal veggie meter	•	•		•	•	•

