Maternal olfactory testing	•	•		•		•
Maternal urine	•	•	•	•	•	•

Maternal cognitive testing	•	•		•	•	•
Maternal stool	•	•		•	•	•
Maternal blood draw	•	•		•	•	•
Maternal actigraphy	•	•		•	•	•
Infant anthropometrics			•	•	•	•
Infant skin folds			•	•	•	•
Infant body composition (PeaPod)			•	•	•	•
Infant stool			•	•	•	•
Infant DXA scan			•			•
Infant diet recalls			•	•	•	•
Breast milk				•	•	
Satisfaction survey (Hfib only)		•				
Process evaluation (Hfib only)		•				

C7a) Gestational weight gain: GWG will be calculated following the NIH LIFE-Moms protocol¹⁰⁶. Self-reported pre-pregnancy weight will be replaced with baseline study measured body weight and subtracted from weight measured at 34 weeks to calculate GWG. When data are missing, we will extract body weight at delivery admission from the electronic medical record. GWG guidelines will be used to classify excessive GWG⁶⁹.

C7b) Questionnaires: Questionnaires will be given to assess maternal pregnancy and infant birth characteristics at study visits, via REDCap surveys, and over the phone throughout the study. Examples include maternal health (medical and obstetric history), self-reported race/ethnic background, income, education, household information (marital status, baby father's health, etc.), hunger and satiety, emotional health, gastrointestinal health, supplement use, alcohol consumption, drug use, infant sex, birth weight, birth length, and gestational age, to name a few¹⁰⁷⁻¹⁰⁹. One survey will ask about liking or disliking of foods to assess perception of taste and olfaction, which can influence what foods people choose to eat. The survey will be taken through a link (https://uconn.co1.qualtrics.com/jfe/form/SV_aVFeLIsOTSVSCzk) which is hosted by the University of Connecticut and the corresponding data will be stored on their server. Once the survey has been scored, the results will be sent to the study team. No identifying information except a participant ID will be included in the survey.

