C7f) Anthropometry: Body weight will be assessed on the same calibrated scale (Detetco Scales, Webb City, MO) throughout the study duration for the mother and a calibrated pediatric scale for the infant (Scale-Tronix, White Plains, NY). Height will be measured using a wall mounted stadiometer (Accu-Hite, Seca Corp, Hanover, MD) for the mother and length using a length board (Shorr Productions) for the infant. Two or more measurements will be taken, and the average recorded. Infant head and waist circumferences will be measured two or more times, and the average recorded.

C7g) Maternal and infant body composition: Maternal body composition will be assessed using the Selinger four-compartment model¹¹³ at baseline, end of intervention, and 2, 6, and 12 months postpartum. The 4C model includes body mass, body volume, total body water, and bone mineral content. Percent fat will be determined by the equation: $\%FM = ([2.747/BD] - [0.714*TBW/BW] + [1.129*B/BW] - 2.037) \times 100$; where BD is body density in kg/L, TBW is total body water in L, B is bone mineral in kg, and BW is body weight in kg¹¹. Body mass will be measured by an electronic scale (Detetco Scales, Webb City, MO). Body volume will be assessed via air displacement plethysmography²⁶ (BodPod®; CosMed, Concord, CA)¹¹⁴. Women will wear minimal tight-fitting clothing (e.g. one-piece swimsuit) and a fitted hat. Body density will be calculated as body mass/body volume. Total body water will be assessed using bioelectrical impedance analysis (BIA; Tanita, Inc., TBF-310, Tokyo, Japan)¹¹⁵. Bone mineral content will be measured by dual-energy X-ray absorptiometry (DXA; GE Healthcare, Lunar Prodigy, Madison, WI). DXA is contraindicated during pregnancy since radiation emission is considered harmful to the fetus¹¹⁶, so bone mineral content will be assessed at 2 weeks postpartum^{1,11,117}. Infant body composition will be assessed via air displacement plethysmography²⁶ (PeaPod®; CosMed, Concord, CA)¹¹⁴ at 2 weeks, 2 months, and 6 months (if infant ≤ 10 kg). Infants are tested nude with a tight fitting hat³. Our Pea Pod® system has the larger tray allowing testing of infants with a body weight up to 10 kg.

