C7i) Process evaluation: Data will be collected throughout the intervention to assess barriers to recruitment and study retention, participant acceptability and intervention adherence, and how well the intervention was implemented. Participants that drop will be contacted and asked to complete a brief interview to provide feedback. Semi-structured interviews will be conducted at the final assessment (34 wks). Participants will be asked about their perception of the intervention including both positive and negative aspects and any challenges that were encountered, pros and cons of using group video counseling to promote healthy behaviors during pregnancy, and their overall satisfaction with the intervention. Interviews will be audio recorded and transcribed verbatim. Comments will be coded, categorized into themes and used to refine and further develop future interventions.

C7j) Safety monitoring: All subjects will be given a body weight scale and report body weight weekly. This allows close supervision of progression of each participant to ensure the intervention is not overly effective and all women are gaining adequate body weight. If a woman gains or loses more than 5 lbs over a two-week period, she will be flagged and contacted. If she is in the Hfib group, total weight gain recommendations will be reviewed and her dietary habits and fiber intake will be reviewed and reinforced. Rapid weight changes or any other safety concerns will be reviewed by our study physician for safety purposes. The participant's provider will be notified if physician deems necessary.

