C7t) Breastmilk analysis: Participants who choose to breast feed will be asked to pump one breast until empty, homogenize the breastmilk by stirring, and return 20-mL to the study team for nutrient analysis. Participants will be asked to do this at 1 month, 2 months, 3 months, 4 months, 5 months, and 6 months, freeze it, and return it to the study team at the 2-month and 6-month visits. The remainder of the breastmilk collected can be kept by the participant and fed to their infant. Any leftover sample after initial nutrient analysis will be banked for future evaluations related to nutrition and brain health and KUMC.

C8) Steps to maximize adherence and retention: We will be using incentives for study visits, incentives for reporting goals, and regular short-term performance and feedback.

C8a) Incentive system: Participants will be compensated \$100 for each of the 6 study visits: baseline, end intervention, 2 weeks postpartum, 2 months postpartum, 6 months postpartum, and 12 months postpartum totaling up to \$600 for completion of all visits. Participants asked to return for repeat infant DXA (no more than 2 at each study timepoint) will be compensated an additional \$50. Compensation will be provided on a ClinCard, which is given at enrollment. After each visit study staff will load their unique card number with the respective pay. Participants can use the card anywhere Mastercard is accepted, and study staff does not have access to where the money will be spent.

C8c) Monitoring retention: When participants miss a session or reporting of behaviors, they will be contacted and a standardized protocol according to attendance and adherence demands will be used to make every effort to retain the participant or encourage reporting. This will be documented and used for program evaluation.

C9) Statistical analysis: The purpose of this study is to attain feasibility data therefore the small sample size does not afford the power to detect significance but to identify promising trends and relationships.

Analysis for Aim 1 H1: A t-test will be used to determine if there is a difference in maternal weight gain and fat accretion between the two groups.

Analysis for Aim 2 H2: A t-test will be used to quantify if there is a difference in fiber intake and dietary quality between the two groups.

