The women will be informed that the purpose of the study is to determine if a high fiber diet can help them gain the right amount of weight during pregnancy and that they will be placed in an intervention or control group. They will be told that if they participate in the study, regardless of their group assignment, that they will need to be seen two times during their pregnancy and four times after pregnancy. Further, they will be told if they are randomized to the intervention group they will be required to attend weekly video calls and report goals weekly to the study coordinator for 18 weeks.

Consent forms and HIPPA disclosure information per IRBs will be given to all subjects and their signatures witnessed. The consent forms will include a description of the study, nature of the data collection, the potential benefits and adverse reactions anticipated. Women will be assigned to group by random assignment provided by study statistician. The subjects will be told that their usual care would not be changed, withdrawn, or reduced if they chose to withdraw from the study at any time. The research team personnel will abide by all tenets of the University confidentiality policies, as well as the Privacy Protection for Research Subjects. All research staff will remain current in their NIH required Human Subjects protection and HIPAA certification.

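### The late-pregnancy visit behind both Aim 1 outcomes is dated in two ways, and a missing weight there is replaced by a later delivery weight that the planned t-test treats as equivalent

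*Combined protocol and SAP*

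**What the plan says.** Two parts of the protocol date the late visit at 34 weeks.

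- C7a defines gestational weight gain: "Self-reported pre-pregnancy weight will be replaced with baseline study measured body weight and subtracted from weight measured at 34 weeks to calculate GWG".
- C7i uses the same week for the closing interviews: "Semi-structured interviews will be conducted at the final assessment (34 wks".

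Two other parts tie it to the end of the course.

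- The Table 4 column heading is "End of Intervention: 30-38wks".
- C7g schedules maternal body composition "at baseline, end of intervention, and 2, 6, and 12 months postpartum. The 4C model includes body mass", with no gestational week.

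C2 sets the length of the course: "The intervention will start at 12-20 wks and last 18 weeks, ensuring intervention completion by 38 weeks in pregnancy". The consent information under Adequacy of Protection Against Risks tells women in either group that "they will need to be seen two times during their pregnancy and four times after pregnancy". Only one late-pregnancy visit therefore exists, and it has to supply both the end weight and the end fat mass.

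C7a adds a fallback for weight: "When data are missing, we will extract body weight at delivery admission from the electronic medical record". No fallback is given for fat mass. The Aim 1 analysis in C9 is: "A t-test will be used to determine if there is a difference in maternal weight gain and fat accretion between the two groups". It mentions neither gestational age nor the time between the two measurements.

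**The concern.** Both Aim 1 outcomes are changes from baseline, so their size depends on how long each woman is followed. Under the 34-week rule the interval varies with the starting week. Under the end-of-intervention rule it is 18 weeks for everyone whose baseline falls at the start of the course. The documents do not say which rule governs, or what tolerance applies. It is therefore unclear whether a weight taken at 31 or 37 weeks counts as the 34-week weight or as missing.

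That matters because a missing weight leads to a delivery weight, taken over a longer interval. Usual-care women have no course to finish, so the phrase used for the visit does not locate theirs within the 8-week window. If the interval or the share of delivery weights came to differ between arms, the t-test would attribute that difference to diet.

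**Working it through.** **Inputs from the documents.** Baseline and course start at 12-20 weeks; 18-week course; end visit at 30-38 weeks (C2, Table 4). Pilot gains: usual care 18.4 kg (SD 7.3, n=9), intervention 11.8 kg (SD 4.0, n=14) (Table 1). Pilot losses: 3 of 12 usual care, 0 of 14 intervention (C1). Total sample 56.

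**Assumptions.** 28 per arm. Gain rate 0.30-0.46 kg/week, from Table 1 gains spread evenly over 40 weeks: 11.8/40 = 0.295 and 18.4/40 = 0.46. Delivery at 38-40 weeks. Starting weeks spread evenly over 12-20 where a distribution is needed.

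**1. The plan's own window.** 12 + 18 = 30 and 20 + 18 = 38, so Table 4's window is exactly the starting week plus 18.

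**2. Gap between the two rules.** |start + 18 - 34| = |start - 16| weeks.

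| Start (weeks) | Interval to week 34 | Interval to end of course | Gap |
|---|---|---|---|
| 12 | 22 | 18 | 4 |
| 16 | 18 | 18 | 0 |
| 20 | 14 | 18 | 4 |

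The largest gap is worth 4 x 0.295 = 1.18 kg to 4 x 0.46 = 1.84 kg per woman. With even starts, a visit at start plus 18 falls within 1 week of week 34 for 2/8 = 25% of women and within 2 weeks for 4/8 = 50%. A woman starting at 20 weeks has had 14 of her 18 course weeks by week 34.

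**3. Delivery weight in place of a week-34 weight.** Extra interval 38 - 34 = 4 to 40 - 34 = 6 weeks. Extra gain 4 x 0.295 = 1.18 kg to 6 x 0.46 = 2.76 kg per woman.

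**4. Same rule in both arms.** No bias. Under the 34-week rule the interval has SD 8/sqrt(12) = 2.31 weeks, or 0.68-1.06 kg. Pooled pilot SD = sqrt((8 x 7.3^2 + 13 x 4.0^2)/21) = 5.50 kg. Inflation: sqrt(5.50^2 + 0.68^2)/5.50 - 1 = 0.8%, and sqrt(5.50^2 + 1.06^2)/5.50 - 1 = 1.9%.

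**5. Illustration of unequal fallback use.** If 25% of usual care (3/12) and no HFib women had a delivery weight, mean usual-care gain would rise by 0.25 x 1.18 = 0.30 kg to 0.25 x 2.76 = 0.69 kg. The standard error of the arm difference is 5.50 x sqrt(2/28) = 1.47 kg, so this is 0.2-0.5 standard errors.

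**6. Effect on the test.** The planned t-test was simulated with no diet effect (28 per arm, SD 5.5, 20,000 runs, rates 0.30-0.60 kg/week). It rejected about 5% of the time with 34 weeks in both arms, and 5.6-7.5% of the time with the 25% versus 0% fallback and delivery at 39 weeks.

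The documents give no rate of fat gain, so no figure is offered for fat accretion.

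**The case against.** The best defence is that 34 weeks is only a label for the Table 4 visit. It is the midpoint of 30-38, and C7i attaches it to the process evaluation, which Table 4 lists in the end-of-intervention column. The Specific Aims also describe weight gain as measured before and after the intervention. This is plausible, so the two datings need not be an outright contradiction. But C7a makes the 34-week weight part of the outcome formula and attaches a replacement rule to it, and no tolerance is stated. Even as a label, it leaves an 8-week window.

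C7a also says it follows an outside weight-gain protocol, which may contain a visit window. That cannot be checked here; the formula written in C7a contains none.

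Three stronger readings are tempting, and the documents do not support them.

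- *Usual care is left out of the schedule.* It is not. Table 4 covers both arms, with only two rows marked for HFib alone, and the consent text gives both arms two pregnancy visits. Only the position within the window is unset.
- *HFib is measured at end of course and usual care at week 34.* That would shift the arm difference by 2 weeks (0.6-0.9 kg) if mean baseline were 14 or 18 weeks, and by nothing at 16. No text sets such a schedule: C7a applies 34 weeks to everyone, and the only arm-specific use of it, in C7i, concerns HFib.
- *The pilot shows the fallback will favour HFib.* Its losses were dropouts excluded from Table 1, not women who missed a visit and still supplied a delivery weight. Three of 12 against 0 of 14 is also weak evidence (Fisher exact p = 220/2600 = 0.085). Item (8) on withdrawal further limits later data, so 25% versus 0% is an upper case.

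Finally, C9 describes a feasibility study without power. That limits the consequence, but a trial meant to show promising trends still needs a comparable estimate in each arm.

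**Conclusion.** The point holds as a defect in the definition of the Aim 1 outcomes. The late visit is dated two ways that agree only for a 16-week start and otherwise differ by up to 4 weeks, about 1.2-1.8 kg per woman. The weight fallback adds about 1.2-2.8 kg per woman relative to week 34, and the analysis treats these gains as equivalent.

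Bias between arms is possible but not shown. Timing that is the same in both arms costs 1-2% on the SD. An upper-case imbalance in delivery weights would move the difference by 0.3-0.7 kg. All the kilogram figures rest on the assumed gain rate, and those for the fallback also on the assumed delivery week. The plan should be corrected because the rule is simple to settle and the outcome is primary; nothing here shows that the trial's comparison is already distorted.

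**What to change.** 1. Set one end-visit rule for both arms and both Aim 1 outcomes, for example 18 weeks after the woman's own baseline visit, with a stated window. Because groups start together after baseline testing, the window must be wide enough to be workable. Amend C7a and C7i to use that visit; Table 4's windows already fit.
2. When the visit weight is missing, use the weekly reported home weight nearest the date the visit was due. Both arms already report weekly.
3. Keep the delivery-admission weight for a sensitivity analysis that accounts for the actual interval. Report the number of home and delivery weights used, by arm.
4. In C9, replace the Aim 1 t-test with a linear model of arm plus gestational age at baseline. This term alone does not correct for delivery weights, which is why item 3 moves them out of the main analysis.

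If the sponsor prefers 34 weeks, apply it to weight and body composition in both arms, change Table 4 and C7g to match, and state that up to 4 course weeks go unmeasured for starts after week 16.

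The cost is wording and some scheduling discipline, with no new visit or measurement. Home weights are self-reported. Some women with a 20-week baseline will deliver before a 38-week visit and have no late fat measure, a risk Table 4 already carries.

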Ideally, women would enter pregnancy at an appropriate body weight. However pre-conception interventions have yet to be tested, proven viable, or successful. Many primary care physicians do not counsel patients on weight loss, diet, and exercise due to inadequate resources and feelings of ineffectiveness⁷⁰. This highlights the importance of interventions during pregnancy. Pregnancy is an important time period that “programs” disorders and a time when many pregnant women are more likely to adopt healthy behaviors for the well-being of their baby¹⁴. Several interventions have been completed with varying success and are discussed below.

A2) Intervention lack of success: Four meta-analyses^{16,18,20,24} and five systematic reviews^{15,22-25} show limited success in published interventions. For interventions including diet and physical activity (PA), three⁷¹⁻⁷³ found improvement in rate of adherence to IOM guidelines while ten⁷⁴⁻⁸³ did not see improvements in adherence. Studies compared differences by BMI groups and found effectiveness in normal weight but not overweight/obese participants^{84,85}. Two studies in obese pregnant women provided counseling with a Registered Dietitian at one session⁸⁶ or 10 sessions⁸⁷ focusing on diet and found improved dietary quality⁸⁷ and reduced GWG^{86,87}. The greatest success (80% gained <10.6 kg) was found in a study of overweight/obese women using personalization of diet and PA (walking program using pedometers) and consistent self-monitoring⁷². This study was especially impressive as the intervention started at 16-20 wks and the entire cohort had already gained excessively.

A3) Lessons from prior studies: Failed studies cite poor outcomes were due to PA not being desirable during pregnancy⁷⁹, needing one provider delivering counseling to ensure consistent messages⁷⁴, the intervention was not intensive enough^{75,84,85}, too infrequent of contact^{75,79,84}, the need to emphasize caloric restriction⁸⁴, the intervention started too late⁷⁸ or was too short⁷⁹, the need to involve significant others⁷⁶, and poor adherence^{75,81}. Successful studies were intensive, set calorie and PA goals and used self-monitoring²⁰.

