Analysis for secondary Aim 1 H1: Repeated measures ANCOVA will be used to assess the difference in gut microbiome composition and diversity from baseline to study end between groups.

Analysis for secondary Aim 2 H2: A t-test will be used to determine if there is a difference in infant fat accrual between groups.

Analysis for secondary Aim 3 H3: A t-test will be used to determine if there is a difference in metabolic, inflammatory, and brain health markers.

Process evaluation: A process evaluation will be completed.

C10) Study challenges: A primary study challenge is the recruitment and retention. [name] has completed protocols successfully recruiting participants from the OB clinics at KUMC. [name], KUMC head of OBGYN, reports 1800 annual deliveries take place at KUMC with ~40% overweight. A second challenge is to assure the fidelity of the interventions. [name] will listen to 20% of GBPC sessions and compare the content delivered to a standardized checklist. If less than 80% of content is covered, [name] will re-train the Dietitian. A third challenge is to ensure subjects are attending sessions and reporting behaviors. We had a high degree of weekly reporting in our pilot study and anticipate a similar response rate in this pilot.

C11) Expected results: We anticipate the Hfib intervention will successfully prevent excessive GWG. The Hfib intervention holds promise to be delivered in routine clinical care. If the results are positive, the next study would be to adapt and embed the Hfib intervention in routine clinical care. The literature supports preventing excessive GWG has a high likelihood to greatly improve the health of both mothers and their offspring however there is variable success in published interventions. This supports the need to design and test interventions informed by prior study failures.

C12) Environment: The environment at KUMC is well suited to conduct this research.

References:

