Case Report Forms on all women will include medical information pertinent to the study (e.g., smoking history, blood pressure, pregnancy history, age, race, etc.) in addition to the information directly related to the study (e.g., height, pre-pregnancy and clinic weights, blood pressure, EDD by ultrasound or LMP, etc.). To maintain patient privacy, all case report forms, study reports and communications will identify the patient by the assigned patient number only. The medical record and originals of outcome data will be the source documents for the study. Any changes to the case report forms necessitated because they are odds with source documents will be initialed and dated by the Study Coordinators; and all Case Report Forms will be reviewed and approved by signature of the PI. Data monitors and auditors from the IRBs, and regulatory authorities will have access to the patient's original medical records for verification of data gathered on the case report forms and to audit the data collection process. Subjects will be made aware of persons who may see their protected health information in the informed consent document and may choose not to enroll in the study based on the information provided them in accord with 2003 HIPAA regulations. The patient's confidentiality will be maintained and will not be made publicly available to the extent permitted by the applicable laws and regulations.

Data monitors and auditors from the IRBs, and regulatory authorities will have access to the patient's original medical records for verification of data gathered on the case report forms and to audit the data collection process. Subjects will be made aware of persons who may see their protected health information in the informed consent document and may choose not to enroll in the study based on the information provided them in accord with 2003 HIPAA regulations. The patient's confidentiality will be maintained and will not be made publicly available to the extent permitted by the applicable laws and regulations.

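### C7a classifies a partial, unequal-length weight gain as excessive or not without matching the guideline limit to the weeks measured

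*Combined protocol and SAP*

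**What the plan says.** C7a gives the GWG rule: "Self-reported pre-pregnancy weight will be replaced with baseline study measured body weight and subtracted from weight measured at 34 weeks to calculate GWG". If data are missing, weight at delivery admission is taken from the medical record instead. The section then says "GWG guidelines will be used to classify excessive GWG", with a reference to the 2009 IOM guideline. It names an external trial protocol as the source of the method but does not reproduce it. No threshold, weekly rate or proration step is printed.

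The timing comes from Table 4: "Baseline: 12-20wks" and "End of Intervention: 30-38wks". C2 sets an 18-week intervention starting at 12-20 weeks. C7i, like C7a, places the final assessment at 34 weeks.

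Elsewhere, C7j describes a counselling step in which "total weight gain recommendations will be reviewed". C5c makes gain inside the 2009 IOM range the goal for participants. C11 states: "We anticipate the Hfib intervention will successfully prevent excessive GWG". The case report form holds "height, pre-pregnancy and clinic weights" (Adequacy of Protection Against Risks). C9 lists a t-test for weight gain and no analysis of the proportion gaining excessively.

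**The concern.** The quantity that C7a calls GWG leaves out everything gained before the baseline visit and, unless the delivery fallback is used, everything gained after 34 weeks. The next sentence classifies that quantity by a guideline without adapting the limit to the shorter interval. C7j speaks of total-gain recommendations, and nothing in the protocol mentions a weekly rate for classification. The plainest reading therefore sets a partial gain against a whole-pregnancy ceiling. A2 shows that early gain can be large: in one cited study "the intervention started at 16-20 wks and the entire cohort had already gained excessively".

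Three things are at stake. Women who exceed the guideline may be counted as not excessive. A woman measured over fewer weeks has less opportunity to cross the same ceiling than one measured over more. The resulting proportion would also not be on the scale of the 56% and 78% figures that the protocol quotes. The title, the C5c goal and the C11 expectation all concern excessive gain, so this proportion will be read as evidence even though C9 does not list it.

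**Working it through.** **Inputs.** Baseline 12-20 weeks and end visit 30-38 weeks (Table 4); 34-week end weight and delivery fallback (C7a); 18-week intervention (C2). Pilot GWG in Table 1: usual care 18.4 (SD 7.3) kg, n=9, 78% excessive; intervention 11.8 (SD 4.0) kg, n=14, 29% excessive. Assumed: delivery at 40 weeks.

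**The plan's own figures.** The plan gives no figure for the proportion expected under C7a. The pilot figures do reproduce: 7/9 = 77.8%, 4/14 = 28.6%, and the pooled t-test gives t = 2.81, p = 0.0105, against the printed 0.010.

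**Step 1: window length** (end week minus baseline week).
- To 34 weeks: 34 − 20 = 14 up to 34 − 12 = 22 weeks, a spread of 8 weeks. This is 35-55% of 40 weeks.
- With a delivery weight: 40 − 20 = 20 up to 40 − 12 = 28 weeks, which is 6 weeks longer for the same woman.
- With the Table 4 end visit at start + 18: 12 → 30, 16 → 34, 20 → 38. The visit falls at 34 weeks only for a 16-week start.

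**Step 2: share of total gain captured, f.** Let a share s of 5-20% be gained by week 13, with linear gain from then to week 40. For a week w from 13 on, cumulative share = s + (1 − s)(w − 13)/27; before week 13 it is s·w/13. From baseline to 34 weeks this gives f of about 0.42 (s = 20%, baseline 20 weeks) to 0.74 (s = 5%, baseline 12 weeks). Assuming instead 0-2 kg gained by week 12 and linear gain to week 40, the usual-care mean gives (16.4/18.4)(14/28) = 0.45 up to 22/28 = 0.79. The table below uses 0.5-0.8 as a round working range. At the low end of these derived values the usual-care rate would be lower still.

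**Step 3: cut-off implied by the pilot**, assuming normality and whole-pregnancy pilot gains.
- Usual care: 18.4 − 0.772 × 7.3 = 12.8 kg.
- Intervention: 11.8 + 0.553 × 4.0 = 14.0 kg.

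**Step 4: rate if that cut-off c is applied unchanged to the partial gain.** P = 1 − Φ[(c − f·mean)/(f·SD)], with the SD assumed to scale with the mean.

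| f | Usual care | Intervention | Difference (points) |
|---|---|---|---|
| 0.5 | 16% | 0% | 16 |
| 0.6 | 35% | 0.2% | 34 |
| 0.7 | 51% | 2% | 49 |
| 0.8 | 63% | 8% | 56 |
| 1.0 | 78% | 29% | 49 |

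If the limit is scaled to the same weeks as the gain, c becomes f·c, f cancels, and the rates stay at 78% and 29%.

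**Step 5: effect of the delivery fallback on kilograms.** At the usual-care mean, six extra weeks add 6 × 16.4/28 = 3.5 kg to 6 × 18.4/28 = 3.9 kg. This enters the Aim 1 outcome as well as the class. The pilot lost 3 of 12 controls and 0 of 14 intervention women (C1), so unequal use of the fallback between arms is plausible.

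**The case against.** The strongest reply is that C7a leaves the rule unstated rather than stating a wrong one. It prints no threshold, and the cited guideline or method, neither visible here, may supply a weekly rate or a matching rule. The C7j phrase belongs to counselling, not classification. The A2 remark can even be read as showing that the standard can be applied part-way through pregnancy. This stands to the extent that whole-pregnancy limits are the natural reading and not a certainty. The printed text still has no step that makes the classification valid, and two analysts could report very different proportions from the same data.

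A second reply is that if the Table 4 end-visit weight is used, every window is about 18 weeks and the 8-week spread disappears. That is correct. It contradicts the fixed 34 weeks, however, and it leaves the limit unmatched to the window.

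Third, starting from a measured baseline is sound for Aim 1: it avoids self-report error and excludes gain that the intervention could not have influenced. This stands in full.

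A reader might go further and infer that most excessive gain is missed and that the trial's answer on HFib is therefore wrong. The documents do not support that. Under the same assumptions, half or more of the usual-care cases are lost only when f is below about 0.62, and HFib stays lower at every f in the table. Aim 1 is a between-group difference in kilograms and fat, tested by t-test, and C9 describes a feasibility study without power. Nor does C7a say that BMI category is recomputed from baseline weight.

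**Conclusion.** The point holds as a defect in how the excessive-GWG class is specified. If whole-pregnancy limits are applied to the C7a gain, excessive gain is under-counted in both arms. The pilot's 78% versus 29% would become about 16-63% versus 0-8% for 50-80% capture. Direction is kept, but the size of the difference is not dependable: it may shrink to 16 points or rise to 56, against 49 with full gain. These figures rest on normality, cut-offs back-solved from 9 and 14 women, whole-pregnancy pilot gains, SDs proportional to means, and an assumed f. They show sensitivity and are not a forecast.

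The unequal windows and the conflict between 34 weeks and 30-38 weeks follow from the printed text alone. The roughly 6 weeks added by a delivery weight assumes delivery at 40 weeks. The Aim 1 t-test over a common window does not depend on the cut-off, so the trial's primary answer is not shown to be wrong. Mixing delivery weights into that outcome would break the common window.

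**What to change.** Amend C7a before analysis, as follows.

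- **Aim 1 outcome.** Keep measured weight change from baseline to end of intervention. Reconcile the fixed 34 weeks with the Table 4 visit window, and record gestational age at both weights. Do not mix delivery-admission weights into this outcome without adjusting for the weeks elapsed.
- **Excessive class.** State one rule. Either (a) take delivery weight minus pre-pregnancy weight, for all women, against the guideline's total range, or (b) divide the measured gain by the weeks actually elapsed and compare it with the guideline's weekly rate, if the sponsor confirms that it gives one.
- **BMI category.** Take it from pre-pregnancy weight under either rule.
- **Reporting.** Add to C9 the proportion gaining excessively by arm, with its confidence interval, as descriptive support for C11.

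The cost is protocol wording and a derived variable. Pre-pregnancy weight is on the case report form, and delivery weight is available from the medical record. Under (a) it must be extracted for every woman, not only those with missing data. The drawback of (a) is that it relies on self-reported pre-pregnancy weight and includes gain from before the intervention. Option (b) avoids both but depends on the guideline providing a rate.
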